### Studyprotocol, v.1.3 20.12.2024

#### 5.4.3 Adherence, retention and dropouts

Physical testing days will be scheduled in coordination with participants' individual hospital schedules to the best extent possible. However, attending physical testing sessions may pose challenges for some patients, particularly those experiencing chemotherapy-related side effects, live alone, have scarce resources, or have functional limitations. Thus, some flexibility in the scheduling of physical testing sessions may be necessary. Any deviations from the testing manual will be communicated with an investigator for discussion and consideration of pragmatic solutions with regards to timing. Adherence to the physical testing protocol, adherence to prescribed intensity, modifications made during testing, interruptions, and reasons for dropouts, will be meticulously recorded throughout the study period. Additionally, any adverse events will be documented electronically by investigators following thorough instruction.

#### 5.4.4 Withdrawal of study participants

Participants will be withdrawn from the study if the participant withdraws consent or if the investigators deem that it is in the best interest of the patient due to e.g. unexpected sudden events such as bone fractures, psychological distress or newly diagnosed severe comorbidities during the study period.

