#### 5.4.2 Participants' information and written informed consent

The treating physician, nurse or investigator will inform eligible patients about the option to bring relatives to be informed and invited into the study by one of the investigators, which will take place in a private room within the Department of Clinical Oncology and Palliative Care, ZUH, Næstved. All patients eligible for participation will receive a verbal explanation in clear Danish regarding the study's purpose and procedures, the voluntary nature of participation, the guarantee of anonymity, the confidential handling of data, and the implications of their involvement, as detailed in Appendix 4c (*Retningslinjer for afgivelse af mundtlig deltagerinformation*). Patients will be assured that participating in the study will not affect their standard medical treatment and that they can withdraw their consent at any time without any impact on their future care. The following written materials about the PHILUCA study will be distributed: the 1) participant information sheet, 2) the written consent form, 3) the latest version of the brochure "*Before You Make Up Your Mind: The Rights of a Trial Subject in a Clinical Research Project*," and 4) a document outlining our management of personal data according to Region Zealand guidelines (Appendiks 6 *Oplysningspligt*).

Patients will be offered a minimum of 24-hour for consideration, with the opportunity to discuss participation with relatives. After mutual agreement about a contact timepoint, an investigator will contact the patient to determine participation. If participation is agreed and the consent form is signed, the patient will receive a copy, and the baseline test will be scheduled and performed. Patients who decline to participate in the full PHILUCA study will be asked if they would be willing to participate in a minor part of the study by completing the baseline questionnaire and allow that clinical and treatment data is obtained from their medical journal (see Appendix 5, Samtykkeerklæring). This aims to examine the characteristics of these partial decliners and determine if they differ from full participants. Informed consent will be obtained for this purpose before any data about them is collected and stored. The same data from medical records and the baseline questionnaire will be collected from partial participants as from full participants (see part 7.1).

## Appendiks 2

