### 5.5.1 Measurements and clinical data

**Table 1** shows the outcomes, measurements and sources that will be used in the study period.

Endpoints	Description	Test/sample/source
Primary outcome		
Survival	
 
○ 1-year overall survival
 
○ 5-year overall survival
 
	Medical records Medical records
Exploratory outcomes		
Sarcopenia	
 
○ Muscle strength and mass and change over time
 
	Routine CT-scan (baseline CT to last performed CT within 12-months after diagnosis) & bioimpedance analysis
Cachexia	
 
○ Stages of cachexia and change over time
 
	Muscle mass (by routine CT-scan and bioimpedance analysis), abnormal biochemistry by routine blood samples and weight loss
Chemotherapy completion rate	
 
○ Mean RDI in %
 
○ Number of patients with an RDI < and <math>\geq 85\%</math>
 
○ Dose-limiting toxicity (DLT) DLT defined as 'switching treatment', 'treatment delay' (<math>\geq 3</math> days from initially planned), 'treatment de-escalation' (dose reduction <math>\geq 15\%</math> of platinum agent), early treatment termination, and hospitalization <math>\geq 1</math> day, all due to chemotherapy-induced side effects.
 
	Medical records
Treatment complications	
 
○ Complications related to surgery, radiotherapy, immunotherapy and targeted therapy.
 
	Medical records
Biomarkers	
 
○ Routine blood tests of plasma CRP and serum-albumin to diagnose cachexia and haematological toxicities
 
	Medical records
Changes in body composition	
 
○ Total muscle and fat mass
 
	Routine CT-scans Bioimpedance analysis

## Appendiks 2

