### Studyprotocol, v.1.3 20.12.2024

01.09.2024 to 01.09.2027. If patients decline participation, all information stored will be deleted immediately.

After written informed consent has been obtained from participants at baseline the medical records will be reviewed by an investigator at regular intervals during lung cancer treatment to collect data on sociodemographic characteristics, anthropometrics, health status, functional status, and clinical information on cancer type and cancer treatment. These include:

- Ordinary personal information; name, address, phone number, email, cohabitation status, employment status, age and sex.
- Sensitive personal information; CPR number, cancer type, cancer treatment, body mass index, body surface area, information on the degree of treatment completion and complications, physical or cognitive comorbidities, CT scan images, PS, time since cancer diagnosis, results from standard blood tests.

The patient's consent gives the investigator and their representative direct access to this information to conduct, monitor, and audit the study. The information from medical records is collected with the aim of investigating whether muscle mass, strength, and function are related to treatment tolerance. The medical records will be reviewed at the end of the study by one of the investigators to extract data on recurrence and survival for a period of up to 1 year and 5-years after lung cancer diagnosis. The data will be handled with confidentiality according to Part 7.2 and used for descriptive statistics of participants and in multivariate analyses of outcomes in a pseudonymised form. Participants who initially provided informed consent and had performed baseline measurements, but were later found not to have lung cancer will contribute with data for comparison analysis between people with and without lung cancer on variables such as sociodemographics, clinical characteristics, baseline physical function and body composition, and survival. No additional measurements beyond baseline testing will be conducted for this cohort. All data will be securely handled in compliance with ethical and confidentiality standards.

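### Section 5.4.4 does not separate ending study tests from ending record follow-up, so patients withdrawn by an investigator on health grounds can drop out of the record-based survival and treatment analyses

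*Protocol*

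**What the plan says.** Section 5.4.4 gives two routes out of the study. The first is the participant's own decision: "Participants will be withdrawn from the study if the participant withdraws consent". The second is the investigator's: "if the investigators deem that it is in the best interest of the patient due to e.g. unexpected sudden events such as bone fractures". The examples in full are "unexpected sudden events such as bone fractures, psychological distress or newly diagnosed severe comorbidities during the study period". Both routes lead to the same result, withdrawal from the study. Nothing is said about records afterwards.

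Table 1 in section 5.5.1 lists "1-year overall survival" and 5-year overall survival as the primary outcome, with medical records as the source. Chemotherapy completion and treatment complications have the same source. Section 7.1 sets the timing: "The medical records will be reviewed at the end of the study by one of the investigators to extract data on recurrence and survival". It also gives the basis for access: "The patient's consent gives the investigator and their representative direct access to this information".

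For two other groups the protocol does keep record data without further testing. Section 5.4.2 says of people who decline the full study: "The same data from medical records and the baseline questionnaire will be collected from partial participants as from full participants". Section 7.1 keeps survival data for participants found not to have lung cancer, who have no tests after baseline.

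The sample-size text (section 6.1 and the update on power and sample size at the front of the protocol) starts from 130 patients for the primary analysis. It inflates that number for study withdrawal, first at 28% and then at an observed 19%.

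**The concern.** The events named as examples are health events that plausibly predict death, and they may be linked to low muscle mass and strength, the exposure under study. They can be good reasons to stop physical tests. They do not prevent anyone from reading a medical record. If withdrawal from the study also ends record extraction, the patients lost may be those with the worse course, and they are lost from an outcome that could have been known for nearly everyone.

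Three things are at stake: the number of deaths, and so precision; the survival estimate, if withdrawn patients die more often; and the treatment-tolerance and vulnerability-tool analyses, which need the patients who tolerate treatment poorly. An analysis plan cannot repair this later, because the rule governs which data are collected.

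**Working it through.** **1. The plan's own arithmetic.** Inputs from section 6.1 and the update: 130 patients needed, hazard ratio 2.38, sarcopenia prevalence 50%, power 90%, two-sided alpha 0.05, withdrawal 28% or 19%.

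- 130 / 0.72 = 180.6 (stated: 180)
- 130 / 0.81 = 160.5 (stated: 160)

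Both figures reproduce to within one patient. The plan therefore budgets to lose 50 of 180 or 30 of 160 patients from the analysis of a record-based outcome.

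**2. Deaths and power.** Schoenfeld's formula gives the deaths needed: 4 × (1.960 + 1.282)² / (ln 2.38)² = 55.9, so 56. The protocol states no death probability. If 130 patients are to yield 56 deaths, it must be 56 / 130 = 43%. Freedman's formula gives 64 deaths, or 49%. Assuming 43%:

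| Patients in the survival analysis | Deaths | Power |
|---|---|---|
| 130 (withdrawn patients dropped) | 56 | 90% |
| 160 (all kept) | 69 | 95% |
| 180 (all kept) | 78 | 97% |

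**3. Survival estimate.** Assume 45% overall 1-year mortality. Let w be the share withdrawn and r the mortality risk of withdrawn relative to retained patients. Mortality in those retained is 0.45 / (w·r + 1 − w).

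| w | r | Mortality, retained | Share of deaths lost | Survival overstated by |
|---|---|---|---|---|
| 19% | 1 | 45.0% | 19% | 0 points |
| 19% | 1.5 | 41.1% | 26% | 3.9 points |
| 19% | 2 | 37.8% | 32% | 7.2 points |
| 28% | 1.5 | 39.5% | 37% | 5.5 points |
| 28% | 2 | 35.2% | 44% | 9.8 points |

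These rows treat all withdrawal as lost. The share that falls under the investigator rule is not given, so they are upper illustrations for this rule alone.

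**4. Hazard ratio.** Assume 160 patients, half sarcopenic, with 1-year survival 0.65 without sarcopenia and 0.65^2.38 = 0.359 with it. Deaths: 80 × (0.35 + 0.641) = 79.3. Remove a share of each group, with 90% of those removed dying within the year, and take the ratio of the log survival proportions in those who remain. For 20% and 5% withdrawn, sarcopenic survival becomes (28.7 − 1.6) / 64 = 0.423 and the other (52 − 0.4) / 76 = 0.679, so HR = ln 0.423 / ln 0.679 = 2.22.

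| Withdrawn, sarcopenic | Withdrawn, other | Hazard ratio (true 2.38) |
|---|---|---|
| 20% | 5% | 2.22 |
| 10% | 2.5% | 2.32 |
| 20% | 8% | 2.39 |
| 10% | 5% | 2.45 |
| 20% | 10% | 2.52 |
| 15% | 10% | 2.66 |
| 10% | 10% | 2.78 |

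The direction turns on the ratio of the withdrawal shares. In this model a ratio of 4 to 1 pulls the hazard ratio down, about 2.5 to 1 leaves it unchanged, and lower ratios push it up. The protocol gives no such ratio.

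**The case against.** The best defence is that nothing is lost. No section says that record extraction stops at withdrawal or that withdrawn patients leave the survival analysis. Access rests on consent, which an investigator's decision does not revoke, and section 7.1 can be read to cover everyone who consented. Section 5.4.2 shows that record-only participation is already accepted. Section 5.4.3 promises that "reasons for dropouts, will be meticulously recorded throughout the study period", so affected patients could be traced. The update counts 130 patients available at the 3-month visit, which may mean test attendance rather than survival follow-up.

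Much of this stands. A reader might infer that a fracture or new comorbidity removes the patient automatically; the text makes it a matter of judgement, and the events are examples. A reader might also infer that survival data are certainly lost; that is one reading, not a stated rule.

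The defence does not settle the matter. Section 6.1 wants 130 patients remaining at the end of the study, and the update calls that number the requirement for the primary analysis, so the plan's own reckoning counts withdrawn patients as lost. The two groups expressly kept for record data do not include them. Staff following section 5.4.4 have no instruction to extract their records.

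The calculations in the third and fourth steps also drop withdrawn patients from baseline. A time-to-event analysis would normally keep them until withdrawal and then censor them. That would change the figures, but censoring would still be informative if withdrawal is tied to prognosis.

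**Conclusion.** The point holds as a badly fixed rule about data collection, not as a demonstrated bias. Section 5.4.4 merges two decisions that should be separate, and the sample-size text points to the reading under which patients are lost to the primary outcome.

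If they are lost, deaths and precision are lost with them: about 13 of 69 deaths at 160 recruited, on the assumed 43% mortality. Survival is overstated only if withdrawn patients die more often than retained ones; at equal risk it is not biased.

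It is tempting to conclude that the association between sarcopenia and death is pulled towards the null. The documents do not support that. The direction depends on how withdrawal differs by sarcopenia status, which is not reported. Nor is the 19% dropout broken down by cause, so the part due to investigator decisions is unknown and could be small. The size of any bias cannot be derived from the protocol.

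**What to change.** Amend section 5.4.4 to state three things:

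- An investigator-decided withdrawal ends study tests and questionnaires only.
- Record follow-up (survival, treatment delivered, complications, routine CT) continues unless the participant withdraws consent to it.
- All eligible enrolled patients with a baseline exposure measurement stay in the survival analysis.

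For participants already withdrawn by an investigator whose consent is still valid, extract the same record data. Align section 6.1 and the update, so that the allowance for withdrawal is tied to the outcomes that need attendance.

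The cost is a short amendment and a few more record extractions, with no added visit or procedure. When an investigator judges withdrawal to be in the patient's interest remains as it is now.

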#### 5.5 Study measurements

Participation in the study involves measurements of muscle mass (body composition), muscle strength, muscle function, and patient-reported outcomes on lifestyle and social vulnerability factors (only at time of diagnosis) and QoL and frailty. All physical measurements are performed while the patient is at the hospital for treatment or examination. For patients undergoing chemotherapy, physical tests are - in addition to the planned assessments at the time of diagnosis, after 3 months, and after 6 months - also performed before each treatment cycle, but no later than 6 months after the diagnosis. A timeline of data collection is presented in part 5.6.

#### Sarcopenia

A critical challenge for using sarcopenia as a risk factor based on current evidence is the differences in the assessment methods applied in different research fields and clinical settings . In aging and

## Appendiks 2

## Studyprotocol, v.1.3 20.12.2024

clinical populations outside the oncological field, the sarcopenia diagnosis is based on an assessment of appendicular lean soft tissue by dual-energy x-ray absorptiometry (DXA), bioelectrical impedance analysis (BIA) and rarely magnetic resonance . In contrast, sarcopenia is commonly assessed by computed tomography (CT) scans in patients with cancer. CT scans are readily available for many patients with cancer, given their role in diagnosing and monitoring the disease . To account for diverging muscle mass measurements within current literature, muscle mass will be measured by both BIA and CT scans.

The European Working Group on Sarcopenia in Older People (EWGSOP2) updated their 2010 sarcopenia definition in 2018, emphasizing muscle strength as a primary indicator, streamlining diagnosis methods, and advocating for early detection, treatment and increased research .

Muscle strength will be measured by maximal isometric handgrip strength. The cut-off points for handgrip strength (HGS) will be < 27 kg for males and < 16 kg for females.

Muscle mass measured by BIA will be expressed as appendicular lean mass (ALM) with cut-off points for males < 20 kg and females < 15 kg, and ALM/height with cut-off points for males < 7.0 kg/m^2 and females < 5.5 kg/m^2.

[figure not shown]
Muscle mass measured by CT scans by the third lumbar vertebra (L3), since muscle mass and adipose tissue at the L3 are highly correlated with the whole-body measurements , and are a common muscle mass measurement within the context of lung cancer . This cross-sectional area contains visceral and subcutaneous adipose tissue, psoas, and posterior paravertebral muscles, as well as abdominal wall muscles. These images will be analyzed by using the Slice-O-Matic (Tomovision, Montreal, Canada) software which will allow the specification and segmentation of specific tissue. Segmentation describes the process of separating pixels based on their attenuation in Hounsfield units (HU). Structures are labeled on an image by combining attenuation (often using a range of HUs) and anatomic information. When a range of HU values is used, the process is called threshold-based segmentation. The specific HU range selected varies depending on the tissue of interest. By using the HU limits of 29 to þ150 for skeletal muscles (psoas, erector spinae, quadratus lumborum, transversus abdominis, obliquus externus, obliquus internus, and rectus abdominis), 150 to 50 for visceral adipose tissue, and 190 to 30 for subcutaneous and intramuscular adipose tissue. The cross-sectional areas (cm^2) will be calculated for each tissue by the sum of pixels multiplied by the surface

## Appendiks 2

### Studyprotocol, v.1.3 20.12.2024

area. Lumbar Vertebrae 3 Skeletal Muscle Index (L3SMI) will be calculated by dividing muscle mass in  $\text{cm}^2$  by the patient's height in  $\text{m}^2$  ( $\text{cm}^2/\text{m}^2$ ). Low muscle mass by L3SMI determined by CT imaging will be defined by (men  $<55 \text{ cm}^2/\text{m}^2$ ; women  $<39 \text{ cm}^2/\text{m}^2$ ).

Sarcopenia will be present if both HGS and muscle mass are below the cut-off points. Gait speed will be used to distinguish between sarcopenia and severe sarcopenia. Figure 1 presents the algorithm of diagnosing sarcopenia by the EWGSP2:

**Figure 1:** As presented in Meza-Valderrama et. al. (2021).

In addition, through L3 cross-sectional area, a quantification of body composition; muscle mass area, adipose tissue area (visceral, subcutaneous and intramuscular), and muscle attenuation will be obtained. This method presents high sensitivity and specificity for the detection of changes in body composition. Segmentation will be performed by trained researchers; with further evaluation and approval by a board-certified clinical radiologist.

## Cachexia

Cachexia is a multifactorial syndrome with involuntary progressive weight loss as a result of reduction of skeletal muscle mass with or without depletion of adipose tissue. Cancer cachexia is characterized by systemic inflammation and metabolic changes leading to progressive functional impairment. Sarcopenia as an index for cancer cachexia is a matter of debate. There is a lack of consensus on a definition, diagnostic criteria and classification of cancer cachexia. Therefore, two separate definitions will be accounted for in the PHILUCA study, to ensure possible comparison with existing literature:

The International consensus of the definition of cancer cachexia from Fearon et. al. from 2011 will be used in defining cancer cachexia as  $>5\%$  self-reported unintended weight loss within the past six months, or a 2–5 % weight loss with either a BMI  $<20 \text{ kg/m}^2$ , or reduced muscle mass (males,  $<7.3 \text{ kg/m}^2$ ; females,  $<5.5 \text{ kg/m}^2$ ). Further, cachexia can be stratified into following stages.

Appendiks 2  
Studyprotocol, v.1.3 20.12.2024

[figure not shown]

Figure 2: Fearon (2011) definition as presented in Meza-Valderrama et. al. (2021).

To supplement abovementioned, the definition by Evans et. al. from 2008 will be used (Figure 3). Routine blood samples collected during each hospital visit will provide insight into any abnormal biochemistry. Plasma C-reactive protein and serum albumin levels will be used to calculate the modified Glasgow Prognostic Score (mGPS).

[figure not shown]

Figure 3: Evans (2008) definition as presented in Meza-Valderrama et. al. (2021).

Appendiks 2  
Studyprotocol, v.1.3 20.12.2024

## Frailty

Frailty is a multidimensional clinical condition characterized by a decrease in biological reserve capacity leading to increased vulnerability and reduced ability to resist stressors such as illness, falls, or any circumstances that affect mental and physical well-being. Frailty will be assessed by an investigator using the 9-point Clinical Frailty Scale (CFS), according to the definition by Rockwood. A frailty score  $\geq 5$  indicated the presence of frailty.

### 5.5.1 Measurements and clinical data

**Table 1** shows the outcomes, measurements and sources that will be used in the study period.

Endpoints	Description	Test/sample/source
Primary outcome		
Survival	
 
○ 1-year overall survival
 
○ 5-year overall survival
 
	Medical records Medical records
Exploratory outcomes		
Sarcopenia	
 
○ Muscle strength and mass and change over time
 
	Routine CT-scan (baseline CT to last performed CT within 12-months after diagnosis) & bioimpedance analysis
Cachexia	
 
○ Stages of cachexia and change over time
 
	Muscle mass (by routine CT-scan and bioimpedance analysis), abnormal biochemistry by routine blood samples and weight loss
Chemotherapy completion rate	
 
○ Mean RDI in %
 
○ Number of patients with an RDI < and <math>\geq 85\%</math>
 
○ Dose-limiting toxicity (DLT) DLT defined as 'switching treatment', 'treatment delay' (<math>\geq 3</math> days from initially planned), 'treatment de-escalation' (dose reduction <math>\geq 15\%</math> of platinum agent), early treatment termination, and hospitalization <math>\geq 1</math> day, all due to chemotherapy-induced side effects.
 
	Medical records
Treatment complications	
 
○ Complications related to surgery, radiotherapy, immunotherapy and targeted therapy.
 
	Medical records
Biomarkers	
 
○ Routine blood tests of plasma CRP and serum-albumin to diagnose cachexia and haematological toxicities
 
	Medical records
Changes in body composition	
 
○ Total muscle and fat mass
 
	Routine CT-scans Bioimpedance analysis

## Appendiks 2

